6. TRIAL DESIGN

6.1 TRIAL CONFIGURATION FULL RCT

Study design: Parallel-arm multicentre RCT with one-year internal pilot and two-year long-term extension phase.

Setting: primary care.

Main trial:

6.1.1 Primary outcome measure

• Number of gout flares in the first 2 years

6.1.2 Secondary outcome measures

- Number of gout flares in months 1-12
- Number of gout flares in months 13-24

Page 28 of 71

Treat to target in gout Protocol Final Version 1.1 date 29 May 2019

- Tophus count,
- Size of largest tophus,
- Daily pain score during gout flare,
- EQ-5D-5L during gout flares,
- GIS measured after flare resolution,
- Serum urate level: proportion hitting the target serum urate level (<360 µmol/L) at year 1 and 2,
- Serum urate level as a continuous variable at year 1 and 2,
- EQ-5D-5L between gout flares,
- ULT (name and dose),
- Treatment satisfaction,
- Returned pill count
- MMAS-8 scale,
- Serum creatinine and estimated GFR,
- Urine albumin creatinine ratio,
- Primary-care consultations for gout,
- Hospitalizations due to gout,
- Other prescriptions for treating flares of gout,
- Investigations for gout,
- Incident cardiovascular diseases, hypertension, diabetes,
- Incidence or progression of CKD,
- Death,
- Adverse events (AE), and
- Cost-effectiveness

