7. TRIAL STUDY TREATMENT AND REGIMEN

7.1 Treatment in intervention arm:

Allopurinol-based treat-to-target ULT is the healthcare technology being assessed. It will be delivered by practice nurses trained in delivering and managing a protocol driven allopurinol-based treat-to-target regimen.

The steps of the treat-to-target ULT protocol are consistent with national and international recommendations and recent studies [12–14, 34–35]. These are:

 Allopurinol commenced at a dose of 100 mg/day at the baseline visit in the experimental arm. Participants already on sub-therapeutic dose of allopurinol will have its dose increased by 100 mg/day. Individualized education about gout and principles of management including treat-to-target-ULT discussed. Lifestyle riskfactors of gout discussed. Advice for improving them provided as adjuncts to treatto-target-ULT. Arthritis Research UK (recently renamed Versus Arthritis) leaflet on

> Page 37 of 71 Treat to target in gout Protocol Final Version 1.1 date 29 May 2019

gout provided.

- Participants of Han Chinese, Thai or Korean ethnicities will be commenced on Febuxostat 80 mg/day as first line ULT, as they are at a high risk of developing DRESS syndrome from Allopurinol treatment.
- A booklet containing study contact details, and a table for recording current ULT dose, serum urate level, date of next serum urate blood test, and date of next repeat ULT or flare prophylaxis prescription will be provided to participants in the intervention arm.
- Serum urate measured after 4 weeks, as serum urate is a negative acute phase reactant [13] and the urate level commonly reduces during a flare. If a participant is experiencing gout flare at this time, the visit will be postponed till 2 weeks after the flare has resolved completely. This is a treatment visit and will be conducted by general practice nurses, phlebotomists or other suitably trained staff.
- Allopurinol dose increased by 100mg/day if the serum urate is ≥360 µmol/L at week 4.
- Process repeated approximately 4-weekly until serum urate is <360 µmol/L, or maximum licensed or tolerated dose of allopurinol reached.
- Allopurinol discontinued if unable to achieve serum urate <360 µmol/L due to side effects or intolerance of high doses, or failure to do so despite maximum licensed dose, and febuxostat 80 mg/day started as per the NICE Technology Appraisal 164.
- The dose of febuxostat increased 4 weeks later to 120 mg/day if the serum urate ≥360 µmol/L.

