7.6 Data collected at research assessments

The research nurse in each region will collect data from study participants at the baseline, year 1 and year 2 research assessment visits.

	Research assessment				
	Screening	Baseline	Year 1	Year 2	
Sex	Х				
Date of birth	Х				
Serum urate	Х		Х	Х	
Serum creatinine	Х		Х	Х	
Inclusion criteria	Х				
Exclusion criteria	Х	Х			
Prescription drugs		Х	Х	Х	
Comorbidities		Х	Х	Х	
Body mass index		Х	Х	Х	
Blood Pressure		Х	Х	Х	
Tophus count		Х	Х	Х	
Tophus size		Х	Х	Х	
Urine collection		Х	Х	Х	
Side-effects to ULT			Х	Х	
GIS ¹		Х	Х	Х	
EQ-5D-5L		Х	Х	Х	
TSQ ²			Х	Х	
MMAS-8 ³			Х	Х	
Pill count		Х	Х	Х	
Gout flare and					
Healthcare use diary		Given	Collected	Collected	

Table 11: Research assessments

¹Gout impact scale, ²Treatment satisfaction questionnaire, ³Morisky Medication Adherence Scale-8.

If a study participant brings any medication to the year 1 and year 2 research assessments that are in excess of their requirements and need disposing off, the research staff, after completing the pill count, will advise them to return the excess medications to their local NHS pharmacy from which it was dispensed.

Page 44 of 71 Treat to target in gout Protocol Final Version 1.1 date 29 May 2019

7.7 Data collected from GP surgery:

Data about serum urate, current ULT and flare prophylaxis treatment (name and dose), any temporary treatment discontinuations and reasons, side-effects, and recommended treatment if applicable (name and dose) will be collected by general practice staff at each dose increase visit in the intervention arm as part of usual medical care.

Data about the following variables will be collected from GP surgery records at year 1 and year 2 research assessment visits, along with their dates. This will be collected by GP surgery staff or the local research staff depending on local preference at the GP surgery.

Serum urate (results, dates)

ULT prescriptions (name, daily dose, duration, dates of prescription)

Flare prophylaxis prescriptions (name, daily dose, duration, dates of prescription)

GP surgery consultations for flares (dates)

GP telephone consultations for flares (number, dates)

Out-of-hours emergency GP surgery attendance for flares (dates)

Flare treatments (name, daily dose, total quantity, dates of prescription)

Referral to hospital outpatient clinic for gout (dates of referral)

Hospitalization for gout flare (number, admission and discharge dates)

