Loss of productivity during gout flares: Information about the number of days on which gainful paid employment was lost during each flare will be recorded in the gout flare diary.

Healthcare utilisation for gout during flares: Medicines taken for gout flare, GP visits, A&E visits, out of hours-GP visits, home GP visits, hospitalization, number of days hospitalized.

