7.9 Compliance

Data on total number and dose of ULT prescriptions issued in the preceding 12 months will be collected at each research visit, i.e. at years 1 and 2, and any unused ULT tablets counted. These will be used to calculate the medication possession ratio (MPR). The eightitem MMAS-8 will be completed at year 1 and year 2 research assessment visits.

7.10 Data collection in long-term extension phase:

Participants will continue to provide data about the occurrence of flares after their two-year research assessment visit for an additional two-year period. This will be in the form of a text message or paper diary depending on participant preference.

The GP surgery staff will search their records for GP consultations or hospitalizations due to gout, ULT prescription, other prescriptions for treating flares of gout, investigations, new diagnosis of cardiovascular diseases, hypertension, diabetes, incidence or progression of CKD, or death two years after each participant's last visit.

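### Gout investigations are a 2-year secondary outcome, but the year 1 and year 2 record extraction collects no test except serum urate

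*Protocol*

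**What the plan says.** Section 6.1.2 names "Investigations for gout" as a secondary outcome of the main trial, and the synopsis repeats it in its full-trial list. Section 6.3.2 names it again, separately, for the long-term extension. No section defines which tests count or in what unit.

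The data for years 1 and 2 come mainly from two sources:

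- **GP records (section 7.7).** The list opens with "Data about the following variables will be collected from GP surgery records at year 1 and year 2 research assessment visits, along with their dates". The items cover prescriptions, consultations, out-of-hours and A&E attendance, outpatient referral, hospitalization and side-effects. The one test on it is "Serum urate (results, dates").
- **Participant diary (section 7.8).** The healthcare-use items are "Medicines taken for gout flare, GP visits, A&E visits, out of hours-GP visits, home GP visits, hospitalization, number of days hospitalized".

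For the extension, section 7.10 has surgery staff search for, among other things, "ULT prescription, other prescriptions for treating flares of gout, investigations, new diagnosis of cardiovascular diseases, hypertension, diabetes". That search takes place two years after each participant's last visit.

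On urate testing, section 7.1 has the level measured after 4 weeks of treatment in the intervention arm and then says "Process repeated approximately 4-weekly until serum urate is" below 360 µmol/L or the highest licensed or tolerated allopurinol dose is reached. Section 7.2 gives control participants the screening, baseline, year 1 and year 2 visits only.

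**The concern.** An outcome listed for 2 years needs a matching item in the 2-year data collection. If the section 7.7 list is used as it stands, tests other than urate that GPs or hospitals order for gout during years 1 and 2 are not captured in either arm. An analysis plan can later define the measure, but it cannot supply tests that were never extracted.

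The one test that is captured is driven partly by allocation, because serial urate measurement is a component of the intervention. A urate-only comparison could show more investigations under treat-to-target even if testing prompted by flares had fallen.

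**Working it through.** The plan gives no figure for this outcome, so the check sets the outcome list against every place where year 1 and year 2 data could arise, and then counts the urate tests the protocol orders in each arm.

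**Step 1: is there a data source for investigations in years 1 and 2?**

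| Source | What it records | Gout investigations? |
|---|---|---|
| Section 7.7, GP records at years 1 and 2 | Urate, prescriptions, consultations, attendances, referrals, admissions, side-effects | Serum urate only |
| Section 7.7, dose-increase visits | Urate, treatment, discontinuations, side-effects | Serum urate, intervention arm only |
| Section 7.8 and Table 9 footnote 6, diary | Attendances, medicines, hospital days, impact scale | None |
| Table 11, research assessments | The trial's own samples and measurements | Trial urate and creatinine only |
| Section 8.3, CKD definition | Earlier creatinine when eGFR is below 60 ml/min | None (renal test) |
| Section 8.4, economic data | Gout-related resource use taken from the diary | None beyond the diary |
| Section 7.10, extension search | Investigations named as a search item | Yes, but in the extension and with no stated look-back |

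The neighbouring outcomes in section 6.1.2 (primary-care consultations, hospitalizations, flare prescriptions) each have a matching item in section 7.7. Gout investigations do not, although section 7.10 names them. Table 12 shows the same gap: it has rows for consultations, hospitalizations and prescriptions, and none for investigations.

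**Step 2: how many urate tests does the protocol itself order after randomization?**

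Inputs: Table 9 has treatment visits at weeks 5, 9, 13, 17, 21, 25 and 29, which is 7 visits. Its footnote 4 makes the later urate tests conditional on the previous value being at or above 360 µmol/L. Table 11 puts urate at years 1 and 2 without distinguishing arms.

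- Control arm: 2 tests (year 1 and year 2).
- Intervention arm, target reached at the first treatment visit: 2 + 1 = 3 tests.
- Intervention arm, all scheduled treatment visits used: 2 + 7 = 9 tests.
- Excess in the intervention arm: 3 − 2 = 1 up to 9 − 2 = 7 tests per participant.

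The 2 research tests cancel between arms, so the imbalance comes entirely from the serial tests. The range applies to a participant who starts treatment and attends. Seven is the limit of the Table 9 schedule, not of the text: section 7.1 continues testing through the febuxostat and uricosuric steps, repeats tests that fall too close to a flare, and reopens titration after a year 1 result above target.

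**The case against.** Four arguments on the other side deserve weight.

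1. **Extra monitoring is part of the strategy.** The trial compares a treat-to-target policy with usual care, so more urate testing is a real consequence and a legitimate part of gout-related resource use. This stands. A reader might infer that any difference in urate tests is merely an artefact, or that the protocol treats fewer investigations as a benefit. Neither follows: the outcome has no stated direction and no row in Table 12.

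2. **Removing protocol tests could itself bias the comparison.** Some 4-weekly tests will replace urate tests that a GP would otherwise have ordered, and such GP tests still count in controls. Comparing the arms only after removing the protocol tests could favour the intervention. This also stands, and is why both versions should be reported.

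3. **Protocol tests can largely be identified already.** Urate dates are collected and dose-increase visits are recorded separately, and how to count these tests could be settled in the analysis plan. That is right for urate. It does nothing for tests that are not extracted.

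4. **The outcome is undefined and minor.** It is one bullet among more than 20, and section 4 places healthcare utilisation among the extension objectives rather than the main-trial ones. If only urate testing was meant, dated data exist. This limits the importance of the point. It does not explain why section 7.10 names investigations and section 7.7 does not.

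A reader might also infer that the protocol orders urate tests in one arm only. Table 11 and section 7.2 show otherwise: the year 1 and year 2 tests apply to both arms. Nor do the documents support a trial-wide total of extra tests, since they give neither the expected number of titration visits nor the share of this trial's intervention arm that will start treatment.

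**Conclusion.** The point holds as a mismatch between a stated outcome and its data collection. Investigations other than serum urate cannot be compared between arms at 2 years from the data the protocol says it will collect. A comparison on urate alone is possible, but would largely reflect the serial tests that define the intervention, with a built-in difference of 1 to 7 tests per treated participant within Table 9.

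This rests on two readings: that the section 7.7 list is complete, as its wording suggests, and that the extension search covers only the extension period, since no look-back is stated. If the extraction form already holds an investigations item, the remedy is only to say so in section 7.7.

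The consequence is limited to one secondary outcome. The primary outcome, the sample size and the power are not affected.

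**What to change.** Add a line for gout investigations, with type and date, to the section 7.7 extraction at years 1 and 2 in both arms, with the same content as the section 7.10 search. Define in section 6.1.2 which tests count. Mark the urate tests required by the treat-to-target schedule, and report the arm comparison both with and without them, noting that some may replace tests a GP would have ordered.

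If the sponsor does not want this, remove the outcome from the 2-year lists in section 6.1.2 and the synopsis and keep it for the extension.

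The cost is one extra line on a record extraction already planned for every participant at years 1 and 2, the time to complete it, and a short definition. No extra visit is needed. It should be settled before the year 1 extractions begin, so that both arms are extracted in the same way throughout.

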6.1.3 Safety outcomes

- New intervention-related AEs reported during the study,
- Discontinuation due to intervention-related AEs.

6.2 INTERNAL PILOT

6.2.1 Outcomes

- Consent rate
- Drop-out rate,
- Missingness of outcome data,
- Serum urate level: proportion hitting target and serum urate level (<360µmol/L) at year 1,
- Serum urate level as a continuous variable at year 1, and
- Gout flares in month 7-12.

6.3 LONG-TERM EXTENSION

6.3.1 Primary outcome measure

• Number of gout flares in years 3-4

6.3.2 Secondary outcome measures

• Primary-care consultations for gout,

Page 29 of 71

Treat to target in gout Protocol Final Version 1.1 date 29 May 2019

- Hospitalizations due to gout,
- Urate lowering treatment prescriptions,
- Other prescriptions for treating flares of gout,
- Investigations for gout,
- Incident cardiovascular diseases, hypertension, diabetes,
- Serum creatinine and estimated GFR,
- Urine albumin creatinine ratio,
- Incidence or progression of CKD, and
- Death.

6.4 RANDOMIZATION AND BLINDING

6.4.1 Randomization and blinding

Randomization will be in a 1:1 ratio, stratified by region, contraindication to or intolerance of colchicine prescription intolerance, using random permuted blocks of 2 to 6. Ten randomization lists will be prepared by the study statistician and stored on a secure server in Keele CTU, to which no members of the trial team will have access. One of these lists will be randomly selected by the database manager for use in the trial.

The trial management group and the TSC will be blind to group allocation; none of these individuals will have contact with study participants. The statistician will not be blind to group allocation, owing to differences in serum urate that will be apparent. Unblinded data will be made available to the DMC where appropriate. In such an event, the statistician will prepare the relevant data summaries and the identity of the treatment groups. Unblinding to the study team will only occur once the main trial analyses have been completed.

Randomization will be during office hours using a secure centralised web-based, automated computer generated randomization system provided by the Keele University Clinical Trials Unit (CTU). Authorised personnel at the trial site will be allocated personalised log in details by Keele CTU, in order to access the randomization system. Alternatively, the research or practice nurse can call Keele CTU and the CTU will perform the randomization on the site's behalf. Authorized staff at the CTU will access the randomization tool to perform randomization and inform the nurse of the allocation. The participants' GP and usual care team will be informed of the participants' allocation verbally and in writing within two working days.

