Eligibility criteria	Inclusion criteria: • age ≥18 years. • ability to give informed consent • meets the clinical American College of Rheumatology/European League Against Rheumatism classification criteria for gout • ≥1 flare of gout in the previous 12 months • serum urate ≥360 µmol/l regardless of current ULT
	 Exclusion criteria: previous side-effects to allopurinol that contraindicate rechallenge dementia, severe psychological disturbance i.e. mental health illness that makes receiving the study information and initial screening questionnaire from GP a stressful experience, unable to comply with study procedures, life expectancy less than 12 months, cancer treatment i.e. surgery, radiotherapy, or chemotherapy in the previous 12 months, solid organ transplant, cirrhosis of liver, autoimmune rheumatic disease, Inflammatory bowel disease, current long-term daily prednisolone defined as continuous use for ≥ 30
	 days or current other immunosuppressive treatments, stage 4/5 chronic kidney disease (CKD), pregnant, breast feeding or planning to become pregnant.
Description of interventions	Intervention: Allopurinol-based treat-to-target ULT. Control: Usual GP care of gout, including ULT.
Duration of study	80 months Each participant in the study for at least four years
Randomization and blinding	Randomization in a 1:1 ratio, stratified by region, prior intolerance to colchicine, using randomly permuted blocks of 2 to 6. The trial management group and the trial steering committee will be blind to group allocation. Study participants will not be blinded. The statistician will not be blind to group allocation, owing to differences in serum urate that will be apparent. Unblinded data will be made available to the data monitoring committee where appropriate. In such an event, the statistician will prepare the relevant data summaries and the identity of the treatment groups. Unblinding to the study team will only occur once the main trial analyses have been completed. Randomization will occur online via a web-based system based in Keele Clinical Trials Unit (CTU).
Outcome measures	Internal pilot: Primary outcome: consent rate

Page 6 of 71

Treat to target in gout Protocol Final Version 1.1 date 29 May 2019

Secondary outcomes: drop-out rate, quality of outcome data, serum urate level as a continuous variable at 1 year, and proportion hitting the target serum urate level (<360 µmol/L) at 1 year, gout flares in months 7-
12.
Full trial:

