6.7 SELECTION AND WITHDRAWAL OF PARTICIPANTS

6.7.1 Recruitment

Trial setting: Primary care.

Recruitment: Primary care and community-based recruitment.

- A. GP surgery lists
- Practice staff will search the GP records electronically to identify people with gout based on either any previous diagnosis, previous colchicine prescription, or current or previous ULT prescription.
- The GP will review the patient list to exclude potentially unsuitable participants. e.g. those with dementia, terminal cancer, and severe enduring mental illness.
- Potential study participants will be posted a covering letter, a participant information sheet (PIS), brief questionnaire to (a) assess eligibility, (b) enquire about willingness to participate in the study and for further contact by the research team to arrange for a screening research visit, (c) enquire about contact details, and a freepost envelope addressed to Keele CTU, by the GP surgery staff.
- In case of non-response after 4 weeks, the GP surgery will send a reminder letter to the participant enclosing the PIS and brief questionnaire.
- B. Local community advertising:

In order to recruit participants who may not have consulted their local GP about gout, we will:

- Put up study posters in participating GP surgeries or local pharmacies to inform people with gout who may not have been identified in GP electronic medical record search,
- Put up study posters in up to ten local community centers in each region, and
- Advertise the study in local newspapers.

The posters and advertisements will signpost people interested in participating in the study to

Page 33 of 71 Treat to target in gout Protocol Final Version 1.1 date 29 May 2019

contact Keele CTU. Keele CTU will then contact them as described above.

Initial screening for eligibility:

- Keele CTU will assess eligibility based on questionnaire responses.
- Details of potentially eligible participants will be passed to the regional trial staff in the East Midlands, West Midlands, and Wessex, based in Nottingham, Keele and Southampton Universities respectively with participant consent and the appropriate data transfer agreements.
- It will be explained to the study participants that their identifiable details will be passed by the Keele CTU to the regional trial staff Nottingham, Keele and Southampton Universities respectively.

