- Staff in the Keele CTU and regional trial staff will arrange for the potential participants to be invited for a screening visit at their GP surgery. Screening visits can also be arranged at the participants' own homes if they are unable to attend the GP surgery due to other commitments, e.g. due to work.

Screening visit: The screening visit will be conducted by the regional trial staff. At the screening visit written informed consent will be obtained, participants' eligibility for participation in the trial will be assessed (see section below), and for those potentially eligible based on verbal enquiry, blood will be collected for measuring serum urate, urea and creatinine.

As serum urate can reduce during a gout flare, care will be taken to schedule screening visits at least 2 weeks after self-reported resolution of the gout flare.

Participants who do not meet the eligibility criteria at the screening visit will be informed and the reason(s) for this will be explained. Similarly, participants who give blood for serum urate and creatinine measurement, and have a serum urate level < 360μ mol/L, or eGFR < 30μ m/min will be explained that they do not meet the eligibility criteria for participating in this study. They will be thanked for their time and contribution and advised to consult their GP for gout flares as usual. It will be explained to them that their data collected so far will be used anonymously in the analysis. Screen failures will be replaced with other participants willing to take part in the study.

It will be explained to potential participants that entry into the trial is entirely voluntary and that their treatment and care will not be affected by their decision. It will also be explained that they can withdraw at any time without having to provide a reason. In the event of their withdrawal it will be explained that their data collected so far cannot be erased and we will seek consent to use the data in the final analyses where appropriate.

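### Small block sizes are printed in an open-label protocol, so staff who follow a stratum's sequence can guess the next allocation better than chance

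*Protocol*

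**What the plan says.** Section 6.4.1 fixes the ratio and the strata: "Randomization will be in a 1:1 ratio, stratified by region, contraindication to or intolerance of colchicine prescription intolerance". The block range is given there too: allocation is made "using random permuted blocks of 2 to 6". The synopsis gives the same block range but words the second stratifier differently: "stratified by region, prior intolerance to colchicine, using randomly permuted blocks of 2 to 6". Section 6.7.1 names three regions, "East Midlands, West Midlands, and Wessex". Three regions by two colchicine levels make six strata. Practice is not a stratum.

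Participants are not blinded (synopsis). Allocation is central and web-based. Authorised site personnel log in, or a research or practice nurse telephones the trials unit and is told the result (6.4.1). On the regional staff's role, section 6.7.1 says "The screening visit will be conducted by the regional trial staff" and places the eligibility assessment at that visit. Section 7.6 says "The research nurse in each region will collect data from study participants at the baseline, year 1 and year 2 research assessment visits". Table 9 in section 7.5 puts randomisation at the baseline visit.

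On the lists themselves, section 6.4.1 says "Ten randomization lists will be prepared by the study statistician and stored on a secure server in Keele CTU". It adds that the trial team has no access to them and that the database manager picks one at random.

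**The concern.** Central randomisation conceals the next allocation only if it cannot be inferred from earlier ones. Short blocks return to balance quickly, so the arm that is behind is the better guess, and knowing the block range sharpens that guess. Here the range is in the protocol that recruiting staff work from, and allocations are known once made.

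A guess matters only if someone can act on it, and some room exists. Consent is taken at screening, before randomisation (6.7.4). Exclusion criteria are checked again at baseline (table in 7.6), and one of them, inability to comply with study procedures, is a judgement (6.7.2). People enrolled but not yet randomised may be replaced (6.7.3). The primary outcome is flares reported by unblinded participants (7.8), so blinded assessment would not offset a difference in who enters each arm.

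**Working it through.** The protocol states no predictability figure, so there is none to reproduce. The check asks how well an observer of one stratum can guess.

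**Inputs**
- Block sizes 2 to 6 (6.4.1, synopsis). With a 1:1 ratio these must be even, so 2, 4 or 6.
- The mix of sizes is not stated. Assumption: drawn at random with equal weights. Other weights and fixed sizes are tried below.
- Stratum length: 466 / 3 is about 155 per region if regions recruit equally (assumption). Lists of 150 were used; lengths of 10 to 140 were also tried.
- Share of results that one person sees: not stated, so varied.

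**Method.** The observer holds a weight w(a, b) on each possible state of the current block, with a places left for one arm and b for the other. The probability that the next allocation goes to the first arm is p = sum of w(a, b) × a / (a + b). The best guess is right with probability max(p, 1 − p). Weights are updated after each result. When a result is not seen, they are updated knowing only that a randomisation took place.

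**Check by hand, one fixed and known size**
- Size 2: (0.5 + 1) / 2 = 75% correct.
- Size 4: (0.5 + 2/3 + 2/3 + 1) / 4 = 2.833 / 4 = 71% correct.

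The simulation returns the same values, and 68% for size 6.

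**Sizes 2, 4, 6 equally likely**

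| Share of stratum's results seen | Correct guesses |
|---|---|
| All | 70% |
| Three quarters | 63% |
| Half | 59% |
| A quarter | 55% |
| None (chance) | 50% |

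With full sight, 59% of allocations can be called at probability 0.75 or more, and about 4% are certain. Over other mixes that include size 2, and shorter strata, correct guesses stay within about 69% to 71%, the strongly guessable share within about 48% to 60%, and the certain share within about 2% to 7%.

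A cruder rule, guessing whichever arm is behind among the results seen, also gives 70% with full sight. It drops to 53% when half are seen, 52% for a quarter and 51% for a tenth.

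**Larger blocks, full sight**

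| Sizes (equal weights) | Correct | Probability 0.75 or more |
|---|---|---|
| 2, 4, 6 | 70% | 59% |
| 4, 6, 8 | 68% | 34% |
| 8, 10, 12 | 65% | about 20% |

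**Price of larger blocks.** The largest imbalance within a stratum is half the largest block, so it rises from 3 to 6. If all six strata ended 6 out in the same direction, the arms would differ by 6 × 6 = 36, or 251 against 215. Efficiency relative to equal arms is 4 × 251 × 215 / 466² = 215,860 / 217,156 = 0.994, a loss of 0.6% in that extreme case.

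**The case against.** The strongest reply is that the 70% describes someone who sees everything, and the protocol shows no such person. Randomisation may be done by site personnel, research nurses or practice nurses, across up to 50 practices (8.2), and staffing per region is not given. A reader might infer from section 7.6 that the regional nurse sees every allocation. That section says who collects baseline data, not that one person follows a stratum's whole sequence. This part of the reply stands, which is why the result is given as a range. It does not remove the point: an optimal guesser seeing half the results is still right 59% of the time, although a crude one is close to chance.

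The reply also notes that room to steer is limited. The trials unit does the first eligibility screen (6.7.1), and serum urate and eGFR are laboratory values. That is so, but a judgement criterion and replacement before randomisation remain. Nothing in the protocol suggests staff would misuse them.

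A reader might also infer that the study statistician, who prepares the lists and is unblinded, makes allocations predictable. The documents do not support this. The statistician is given no part in enrolment, another person draws one list of ten, and the trial team cannot reach the stored lists. Having someone else write the lists would be a separation-of-roles preference only.

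Finally, larger blocks lower the average guess rate only from 70% to 65%. That is correct. The larger gain is in the strongly guessable share, which falls by about two thirds.

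**Conclusion.** The point holds as a weakness of concealment that is easy to remove. Printing block sizes of 2 to 6 in an open-label protocol with two stratifiers lets staff who follow a stratum guess the next allocation better than chance. The rate is about 70% correct with full sight and 55% to 63% with sight of a quarter to three quarters. These figures assume that sizes 2, 4 and 6 are mixed at random with equal weights and that the guesser is optimal. Few allocations, about 4%, are ever certain.

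The documents do not show that any guess would be acted on. A reader might wish to convert the guess rate into a bias in flares. That would need the difference in expected flares between steered and unsteered participants, and a rate of successful steering. The protocol gives neither, and the primary model adjusts for prior-year flares (8.3), so no such figure is offered.

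The two definitions of the colchicine stratifier are a real inconsistency but have no bearing on predictability. Someone with a contraindication but no prior intolerance falls in different strata under the two wordings, and the factor enters the primary model (8.3).

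**What to change.** 1. Delete the block sizes from the synopsis and section 6.4.1, say only that randomly permuted blocks of varying size are used, and hold the sizes in a restricted randomisation document.
2. Drop size 2 and use larger, randomly varying blocks; 8, 10 and 12 is one example.
3. Separately, give the colchicine stratifier one definition, used in the synopsis, section 6.4.1, the randomisation system and the primary model.

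The cost is a setting in the web system and a few sentences of protocol text. Maximum within-stratum imbalance rises from 3 to 6, with negligible loss of precision. If recruitment has begun, removing the sizes from the text cannot undo what staff already know, so the change of sizes matters more than the deletion.
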